This will be a prospective, single masked, randomized, clinical trial, which will be registered with ClinicalTrials.gov. Subjects who meet all study criteria will be enrolled and randomized into the study. Subject randomization will be organized by the data coordinator ([name], MS, PhD) and will follow the general guidance provided by Pucker et al. and the Cochrane Eye and Vision group.¹⁸ [name] will create a randomization schedule utilizing blocking (given the small sample size) and stratification by site to maximize the likelihood that study participants will be equally distributed between the treatment groups and by site. Subject group assignments will be concealed in numbered envelopes and distributed among the sites. After a subject is enrolled in the study and after the masked examiner has left the examination area, the unmasked study coordinator will open the envelope, place the subject in the correct group (artificial tears vs. no treatment) and educate the subject about it. The contents of the artificial tear bottle will be concealed. The unmasked study coordinator will educate the subject how to use the artificial tears (2x/day in each eye; once 10 minutes before and once directly after CL wear), and they will instruct the subject to not divulge any information related to their assigned group to the masked examiner. The study subjects will be instructed to not use other artificial tears or rewetting drops during the study.

Sample Size

CLDEQ-4 scores (Rasch validated version; max score of 18) will serve as the primary outcome for judging if Systane Complete is able significantly improve CL comfort.¹⁹ Data from Pucker et al. suggests that the average CL wearer has a mean CLDEQ-4 score of 7.6 ± 3.8 .¹⁹ A 4-point difference in CLDEQ-4 scores will be considered a meaningful improvement in CL comfort. Therefore, 19 subjects per group will be needed to determine if there is no difference in CL comfort between the Systane Complete and the no treatment groups at the two weeks visit (power = 90%; alpha = 0.05). After adjusting for 20% dropout, a total sample size of 46 subjects (16 subjects/site) will be needed to determine if there is a statistical difference in CL comfort scores between subject groups.

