[name], MS, PhD, Professor and Vice Chairman in the Department of Epidemiology at the University of Alabama at Birmingham, will perform the statistical analyses. All data will be analyzed with SAS Version 9.4 (SAS; Cary, NC, USA). The intention to treat analysis method will be employed. The treatment groups will be compared with respect to demographic and baseline clinical characteristics to ensure that the randomization was successful. T- and chi-square tests will be used when comparing continuous and categorical variables, respectively. If the assumptions of these tests cannot be met suitable alternative

statistical tests (e.g., Wilcoxon Rank Sum Test, Fisher's Exact Test) will be used instead. For the comparison of the primary outcome measures (CLDEQ-4 and UM-VCQoL scores), generalized linear models will be used with the follow-up measurement as the dependent variable and treatment group and baseline measurement used as independent variables. While we do not anticipate any differences between the treatment groups, this method ensures that any comparison between the treatment groups will be independent of even minor differences at baseline. Additionally, these models can account for potential differences between the treatment groups with respect to other characteristics, though we do not anticipate any such differences.

Training of Study Personnel

Prior to enrolling any subjects all examiners will meet at the Southern College of Optometry to complete protocol training developed by [name], OD, PhD. This full investigator meeting will ensure that all study investigators are performing the procedures in the same manner. Investigators will also be required to complete an online proficiency test. Data from each investigator's first subject will also be monitored by [name], MS, PhD for quality control before sites are allowed to enroll additional subjects.

.
.
.
.
.
.
.
.

VI. Conclusions

This project will be the first to evaluate the effectiveness of Systane Complete for the treatment of CLD in a rigorous and controlled manner. This work will also provide some of the first data on the impact of artificial tears on a CL wearer's quality of life. Ultimately, after completion of this study, clinicians will have the information needed to determine if Systane Complete is a suitable off-label treatment for patients who suffer from CLD

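### Baseline significance tests are used to judge the randomization, and between-arm difference is the only stated ground for adding covariates to the primary models, so a 5% error rate cannot be guaranteed

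*Combined protocol and SAP*

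**What the plan says.** Section III, Data Analysis, gives the purpose of the baseline comparison: "The treatment groups will be compared with respect to demographic and baseline clinical characteristics to ensure that the randomization was successful". The next sentence names the methods: "T- and chi-square tests will be used when comparing continuous and categorical variables, respectively". Wilcoxon and Fisher tests are held as alternatives.

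The same paragraph then sets the primary model for CLDEQ-4 and for UM-VCQoL: the follow-up score is regressed on treatment group and the baseline score. It goes on: "Additionally, these models can account for potential differences between the treatment groups with respect to other characteristics", and adds that the authors expect no such differences. It does not list the characteristics, set a threshold, say which version of the model is primary, or call the further adjustment a sensitivity analysis.

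Section III, Randomization & Masking, provides for a blocked schedule stratified by site, with assignments concealed in numbered envelopes. Site does not appear among the model terms in Data Analysis.

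**The concern.** There are three separate weaknesses.

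1. **The test does not answer its question.** If the prepared schedule is followed, any baseline difference is due to chance. A small p-value does not show that randomization failed, and a large one in a trial of this size does not show that it worked.
2. **The covariate set is open, and the reason given for extending it is the wrong one.** A covariate earns its place by predicting the outcome. Here the only stated ground is that the arms differ on it, which is known only once the data are in. The masking described is of the examiner. The documents do not say that whoever chooses covariates will be unaware of the outcome results.
3. **The factor used to stratify is not in the model.** A trial randomized within site would ordinarily be analysed with site as a term.

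At stake is whether the p-value and confidence interval for each primary outcome can be read at face value. With about 38 subjects analysed, one added covariate can move a borderline result.

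**Working it through.** **The plan's own figure.** Section III, Sample Size, uses "power = 90%; alpha = 0.05", "A 4-point difference in CLDEQ-4 scores will be considered a meaningful improvement in CL comfort" and an SD of 3.8 ("the average CL wearer has a mean CLDEQ-4 score of 7.6 ± 3.8"). With n = 2(z_{0.975} + z_{0.90})² (SD/difference)² per group:

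- CLDEQ-4: 2 × (1.960 + 1.282)² × (3.8/4)² = 18.97, rounded up to 19. This agrees with "19 subjects per group will be needed".
- UM-VCQoL: the same formula with SD 4.51 and difference 5 gives 17.1, rounded up to 18, as stated.

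One-sided testing would give 16 and 14, so the promised error rate is 5% two-sided. The trials simulated below have 19 per arm (38 analysed) or 23 per arm (46 enrolled).

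**How often would sound randomization look unsuccessful?** For K independent characteristics, each tested at 5%, the chance of at least one p<0.05 is 1 − 0.95^K.

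| K | Chance of at least one nominal difference |
|---|---|
| 5 | 22.6% |
| 10 | 40.1% |
| 11 | 43.1% |
| 15 | 53.7% |

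The plan does not say how many will be tested. Visit 1 supplies SPEED, acuity, eyelid grade, tear break-up time, staining, Schirmer, two meibomian measures and prior tear use. Age and sex are assumed as the demographics, making 11.

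**Error rate of the primary test.** This comes from simulation with no treatment effect, 20,000 to 30,000 trials per scenario. All of the following are assumptions:

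- ANCOVA on group and baseline score, with a baseline-outcome correlation of 0.5.
- 10 independent normal extra covariates at 19 or 23 per arm, or 1 or 3 of them at 19 per arm.
- These covariates jointly explain 0, 30% or 60% of the variance left after the baseline score (30% or 60% only in the runs with 1 or 3).
- Covariates with a baseline p<0.05 are flagged.

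| How the model is chosen | Type I error |
|---|---|
| Group and baseline score only (10-covariate runs) | 4.85-5.24% |
| Group, baseline score and all 10 covariates, fixed in advance | 4.74-5.22% |
| Flagged covariates always added, not prognostic | 4.8-5.1% |
| Flagged covariates always added, 30% explained | 4.1-4.4% |
| Flagged covariates always added, 60% explained | 3.4-3.7% |
| Better of core and flagged model reported, p<0.05 screen | 5.0-5.9% |
| Better of core and flagged model reported, p<0.10 screen | up to about 6.2% |

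The Monte Carlo standard error at 20,000 trials is √(0.05 × 0.95/20,000) = 0.15 percentage points, so the two rows with models fixed in advance are compatible with 5%.

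The always-add rule is conservative for prognostic covariates because it adjusts in just those trials where chance imbalance would have produced a spurious effect. In the rest it keeps a standard error that is too large. Inflation appears only in the last two rows, where the analyst sees both results before choosing. Site was not part of the simulation.

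**The case against.** The case for the plan has real substance.

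- **The core model is prespecified, and no trigger is written.** The text says the models can adjust further. It does not say that a significant baseline test causes adjustment, and that link is only a natural reading of the order of the sentences. A reader might infer that chance decides the primary model. The documents do not support that: at most, chance or discretion governs optional extra terms.
- **Inflation is not planned.** A reader might infer that the error rate is no longer 5%. A mechanical rule leaves it at or below 5%. Exceeding 5% takes a choice made after seeing outcome results, which the plan does not exclude but does not intend.
- **Larger inflation figures describe something else.** Taking the smallest p-value over the core model and every single-covariate addition gives about 8-13% in the same simulation. That lets covariates in whether or not the arms differ on them, whereas the plan ties adjustment to difference. The figure should not be charged to this plan.
- **The chance of a flagged difference depends on independence.** Dry-eye measures are likely to be correlated, which would lower the chance for a given number of tests.
- **A baseline comparison is not wholly empty.** Envelopes are held at sites and opened by an unmasked coordinator, so a gross imbalance could hint at an allocation failure, though weakly at this size. Inspecting a descriptive table serves that purpose without a test.
- **Extra covariates do no harm in themselves.** The row with all ten fixed in advance shows this. What matters is naming them beforehand.

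All of these points stand, and they limit the size of the problem. They do not remove it: the authors' expectation of no differences sits poorly with the first table, and if a difference appears the plan gives no rule.

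**Conclusion.** The point holds in a limited form. Baseline significance tests are the wrong tool for judging randomization. The covariate set of both primary models is not fully prespecified, with imbalance as its only stated criterion. Site, the stratification factor, is not named in the model. The consequence is that a 5% error rate cannot be guaranteed, not that it is known to be breached.

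Under the plan's wording, with a p<0.05 screen, the rate lies at about 3.4-5.1% if flagged covariates are always added. It reaches about 6% if the model is chosen after the results are seen, the upper end coming from a looser p<0.10 screen. These sizes depend on the assumed number, independence and prognostic strength of the covariates, none of which the documents give. The effect is modest, but it touches both primary outcomes and is nearly free to remove, so the plan should be changed.

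**What to change.** Three changes to Section III, Data Analysis, made before the data are analysed:

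1. Drop the tests as a check on randomization, together with that stated purpose. Show baseline characteristics by arm descriptively, without p-values.
2. Replace the sentence on other characteristics with wording such as: *The primary model for each outcome contains treatment, that outcome's baseline score and site. Any further covariate is included only if it is prognostic and is named here before the data are analysed.*
3. Add: *Any other adjustment is a sensitivity analysis and cannot change the primary conclusion.*

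The cost is a few lines of text, with no extra subjects, data or procedures. The sponsor gives up the freedom to adjust after seeing an imbalance. Three sites use two degrees of freedom: with 38 analysed, the residual goes from 38 − 3 = 35 to 38 − 5 = 33. In return, the analysis reflects the factor by which the trial already randomizes.

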Aim 2: Determine if Systane Complete is able to improve the quality of life of daily disposable CL wearers. Hypothesis: Subjects who are randomized to the Systane Complete treatment group will have a statistically significant improvement in their University of Michigan Vision Correction Quality of Life (UM-VCQoL) Questionnaire scores compared to subjects who are randomized to the no treatment group.

III. STUDY DESIGN

Subjects

This two-week, two-visit study will be conducted at the University of Alabama at Birmingham (Birmingham, AL, USA), Southern College of Optometry (Memphis, TN, USA), and Lindenhurst Eye Physicians & Surgeons, PC (Amityville, NY). Subjects will be recruited from each site via clinic records, postcards, email, social network postings (i.e., Facebook), and fliers. Adult (>18 years) daily disposable CL wearers who have 20/30 visual acuity or better and who self-report CLD will be recruited for this study. Other CL modalities/wear schedules (e.g., two week and monthly replacement CLs, gas permeable CLs) and non-compliant daily disposable CL users (must replace CLs daily) will be excluded to avoid any potential confounders associated with CL care systems. Subjects will be screened with the Contact Lens Dry Eye Questionnaire (CLDEQ)-8, and subjects who have CLD (CLDEQ-8 scores ≥ 12) will be enrolled in the study.¹⁶ Subjects will be excluded if they have known systemic health conditions that are known to alter tear film physiology (e.g., primary and secondary Sjögren's syndrome), have a history of ocular surgery within the past 12 months, have a history of severe ocular trauma, active ocular infection or inflammation, are currently using Accutane or ocular medications, or if they are pregnant or breast feeding.¹⁷ Subjects with a condition or in a situation, which in the examiner's opinion, may put the subject at significant risk, may confound the study results, or may significantly interfere with their participation in the study will be excluded. Subjects with non-Sjögren's dry eye disease and subjects who have mild corneal scarring (no corneal elevations changes) will be allowed to participate. Subjects who currently use artificial tears will be allowed to participate, though they will be required to not use artificial tears for at least 24 hours before the baseline study visit and during the study.

Randomization & Masking

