The University of Michigan Vision Correction Quality of Life (UM-VCQoL) Questionnaire will serve as the primary outcome for judging if Systane Complete is able to improve a symptomatic CL wear's quality of life.²⁰ McAlinden and Lipson found with this questionnaire that daily disposable CL wearers had a mean OCL-QoL score of 59.86 \pm 4.51.²⁰ A 5-point difference in OCL-QoL score will be considered a meaningful improvement in a patient's quality of life. Therefore, 18 subjects will be needed to determine if there is no difference in quality of life between subjects randomized to the Systane Complete and the no treatment groups at the two-week visit (power = 90%; alpha = 0.05). After adjusting for 20% dropout, a total sample size of 44 subjects (15 subjects/site) will be needed to determine if there is a statistical difference in CL comfort scores between subject groups. Given the larger sample size requirements for the CLEDQ-4, this study will plan to enroll 46 subjects (16 subjects/site).

Surveys and Clinical Tests

Clinical measurement will be obtained from both eyes of each subject and testing will be performed in the below order. Testing order was designed to sequentially administer the least invasive to most invasive test. This methodology will ensure that a previous procedure will have a minimal effect on all subsequent assessments.²¹ Subjects will be asked to report to the study without their CLs on to minimize the effect of CL removal on the study outcomes. Steps 1 through 9 will be completed by the masked examiner.

Visit 1

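### Randomization is stratified by site, but the stated primary model leaves site out; adding it costs almost nothing and protects precision.

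*Combined protocol and SAP*

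**What the plan says.** The Subjects section under Study Design names three sites. Randomization & Masking calls for a blocked schedule with "stratification by site to maximize the likelihood that study participants will be equally distributed between the treatment groups and by site"; it gives no block size.

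For the primary outcomes, Data Analysis states that "generalized linear models will be used with the follow-up measurement as the dependent variable and treatment group and baseline measurement used as independent variables". Site is not among the terms, and no other section brings it into the analysis. Data Analysis then adds that "these models can account for potential differences between the treatment groups with respect to other characteristics". It does not list those characteristics or say whether a model containing them would be primary.

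The Sample Size section sets the scale for judging any loss. For CLDEQ-4 the SD is 3.8, "A 4-point difference in CLDEQ-4 scores will be considered a meaningful improvement in CL comfort", and "19 subjects per group will be needed to determine" the effect with 90% power at alpha 0.05. For quality of life the SD is 4.51 and "A 5-point difference in OCL-QoL score will be considered a meaningful improvement". Planned enrolment is 46, described as 16 per site.

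**The concern.** Stratified blocks make the arms nearly equal within each site, so differences between sites largely cancel out of the treatment contrast. A model without a site term does not use this. Any site variation that baseline does not explain stays in the residual and inflates the reported standard error, although the design has already removed it from the comparison. Confidence intervals are then wider than they need be and the test rejects too rarely.

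What is at stake is precision and some power, not validity. The loss matters most if evaluable numbers fall to the planned 38, where the design has little margin. A smaller matter is the sentence on other characteristics, which leaves the set of adjustment covariates open.

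**Working it through.** **Inputs from the protocol.** Three sites; blocked, site-stratified allocation; CLDEQ-4 SD 3.8 and difference 4; quality-of-life SD 4.51 and difference 5; 19 and 18 per group; 20% dropout.

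**Assumptions, because the documents are silent.** Blocks of 4; baseline–follow-up correlation 0.5 (0.3 and 0.7 as sensitivity); site share *s* of outcome variance from 0 to 20%. Evaluable numbers are 48 (3 × 16, no dropout) or 38 (2 × 19).

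**The plan's own figures reproduce.** With n per group = 2(1.960 + 1.282)² × (SD/difference)²:
- CLDEQ-4: 2 × 10.507 × (3.8/4)² = 18.97, so 19.
- Quality of life: 2 × 10.507 × (4.51/5)² = 17.10, so 18.
- Total: 38 × 1.2 = 45.6, so 46.

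**Hand check of the mechanism** (site effect at follow-up only, 48 evaluable). In units of 3.8², the residual variance with site in the model is (1 − s)(1 − 0.5²). Without site, it gains the between-site sum of squares, 16 × 2 × s, spread over 48 − 3 = 45 degrees of freedom, which is 32s/45.
- s = 10%: 0.675 with site, 0.675 + 0.071 = 0.746 without. Standard error ratio √(0.746/0.675) = 1.051.
- s = 20%: 0.600 with site, 0.600 + 0.142 = 0.742 without. Ratio √(0.742/0.600) = 1.112.

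**Simulation** (40,000 trials per setting; linear models with and without site; two-sided 5% tests). Site effect at follow-up only, 48 evaluable:

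| Site share | SE without site | SE with site | Excess | Type I error without site |
|---|---|---|---|---|
| 0 | 0.955 | 0.956 | 0 | 4.9% |
| 5% | 0.955 | 0.932 | 2.4% | 4.5% |
| 10% | 0.952 | 0.907 | 4.9% | 4.1% |
| 20% | 0.945 | 0.854 | 10.6% | 3.3% |

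Type I error with site is 4.9 to 5.0% throughout. The excesses agree with the hand check (5.1% and 11.2%) to within about half a percentage point. Bias in the treatment estimate was below 0.01 in all settings checked.

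With the same site effect at baseline and follow-up, the excess is 0.5, 1.0 and 2.0% at shares of 5, 10 and 20%, and type I error without site is 4.7 to 5.0%.

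The correlation matters. At a 20% share the excess is 8.8% (follow-up only) and 3.3% (both visits) at correlation 0.3, and 15.2% and 0.9% at correlation 0.7.

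**Power at 4 points, without versus with site, effect at follow-up only:**

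| Setting | Share 10% | Share 20% |
|---|---|---|
| 38 evaluable, 3.8 as total SD | 95.5 vs 96.3% | 96.0 vs 97.8% |
| 38 evaluable, 3.8 as residual SD | 88.1 vs 89.9% | 89.0 vs 92.8% |

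With 48 evaluable the loss is at most about 0.5 point (99.0 vs 99.5% at a 20% share). When the site effect is the same at both visits, power with 38 evaluable differs by no more than 0.2 point.

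**Cost of adding site when it has no effect.** None is measurable with 48 evaluable. With 38, the SE is 1.077 without and 1.084 with site, and power is 94.7 and 94.5%. A noncentral-t calculation at 19 per group, with 3.8 as the residual SD and residual degrees of freedom falling from 35 to 33, gives 88.4 and 88.3%.

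**Second primary outcome.** The standard error ratios do not depend on scale, so they carry over to UM-VCQoL. The planned effect there is slightly larger in SD units: 5/4.51 = 1.11 against 4/3.8 = 1.05.

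**The case against.** The strongest reply is that nothing is invalid. An analysis adjusted for baseline remains valid under stratified allocation, and at worst the omission makes it conservative. The larger figures also need a site effect that appears at follow-up but not at baseline. The outcomes are self-completed questionnaires given two weeks apart, and the examiners are trained together, so lasting site differences in patient mix or climate should show at baseline too. In that case, with 38 evaluable, the standard errors without and with site are 1.058 vs 1.058, 1.033 vs 1.029 and 0.983 vs 0.970 at shares of 5, 10 and 20%: an excess of about 0, 0.4 and 1.3%. The largest power gain also treats 3.8 as a residual SD, whereas Sample Size gives it as the SD of scores among average wearers. Finally, the sentence on other characteristics would permit site.

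Most of this stands as a limit on size. The gain may be close to nil, and the both-visits case is the more natural one. A follow-up-only effect cannot be ruled out, however, for example if sites differ in how they instruct subjects.

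The last argument does not close the gap. The sentence on other characteristics is optional, names no variable and is tied to differences between arms. Stratification is meant to remove exactly those differences for site, so read literally it gives no reason to include it.

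**Conclusion.** The concern holds. The trial is randomized by site, and its stated primary model does not include site. The consequence is possible loss of precision only, with no bias and no excess of false positives. Over assumed site shares of 5 to 20% at baseline correlation 0.5, with 48 evaluable, the standard error excess runs from 0.5 to 2.0% if site differences are equally present at baseline, and from 2.4 to 10.6% if they arise only at follow-up. The power loss at the planned difference runs from nil to about 4 points (89.0 vs 92.8%). That upper end needs a 20% share, a follow-up-only effect, 38 evaluable subjects and 3.8 as the residual SD, all together. The true position is unknown because the documents give no between-site variance, block size or baseline correlation.

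Since including site costs at most about 0.2 point of power when it is irrelevant, the change is worth making, though the trial does not stand or fall by it.

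**What to change.** In Data Analysis, state the primary model for both CLDEQ-4 and UM-VCQoL as: follow-up score = treatment + baseline score + site, with site a fixed effect at three levels. Label any model with further covariates a sensitivity analysis and list those covariates before data are seen.

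This takes one or two sentences and two degrees of freedom. Site is already known for every subject from the randomization, so no new data or procedures are needed.
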